#### 2b. Sample size and power calculations

To investigate the dose-response association between two continuous variables in cross-sectional analyses, we will first categorize the sample into 4 equal sized groups based on the quartiles of the continuous predictor and study the dose response association pattern using one-way ANOVA. With a total sample size of 150 for study Visit I, thus N=37 per group, in such a one-way ANOVA we will have 80 % power to detect a dose response pattern with a difference of 0.25 SD or high in any two adjacent quartiles. When linear association is a good measure to characterize the dose response association between a continuous outcome and a continuous predictor, we will have 80% power to detect a correlation level of 0.227 or higher, in either direction, with a total N=150 and a two-sided alpha error of 0.05.

We will obtain valuable information on LV structure/function outcomes for the cross-sectional visit, as well as for change in these outcomes over 6 months, for 3 groups of study participants, 25 RA patients treated with TNF-antagonist, 25 RA patients treated with triple treatment or alternative, and 15 non-RA participants with otherwise similar characteristics. For continuous outcomes we will obtain mean, standard deviations, and skewness (to inform us whether certain variables may need transformation before analyses so that sample size/power evaluation for future studies may need to be based on transformed data) for cross-sectional as well as the change over time measurements, and the correlations between two consecutive measurements over time. For binary variables we will obtain prevalence estimates and odds ratios as estimates of association between two repeated binary measures over time. Even accounting for a possible 15% drop out rate of participants, the correlation estimate will have precision ranged approximately between within +/- 0.33 for a correlation of 0.50 and within +/- 0.09 for a correlation of 0.90. For prevalence of binary outcomes, our estimate will be ranged approximately from within +/- 17.9% for a prevalence of 50% to +/-10.7% for a prevalence of 90%. To estimate the power of detecting a 24 week (6 month) change in an LV myocardial outcome within the TNF treated RA group, with a 2-sided alpha of 0.05 and N=22 (accounting for possible drop out), we calculated the minimal detectable change based on cross-sectional SDs and various values for within person correlation between outcome measures at subsequent visits based on data from previous studies performed by the same investigator group. For example with a conservative SD of 1.8 L/min for cardiac output (CO) and 4.2 mL/m^2 for stroke volume (SV) and the correlation between subsequent visits being 0.2 we will have 80% power to detect a 24 week (6 month) change of 1.47 l/min for CO or 3.42 ml/m^2 for SV or more in the TNF inhibitor treated RA group. Similarly in order to estimate power for comparing changes between the TNF inhibitor treated group, the triple therapy treated group and the normal control group we based our calculations with comparing the changes between those groups with one way ANOVA assuming a 15% drop out and a 2-sided alpha of 0.05. We will have 80% power to detect any set of 3 group differences/changes if the SD of the changes is 0.444 or greater. We will have 80% power to detect a difference through the 3 group-one-way-ANOVA if the mean 24 week (6 month) change in SV for the TNF inhibitor group is 5.2ml/m^2 or higher while the mean change for the other two groups is 0. To provide a context regarding the number used above as an expected change in SV we would like to mention here that in our pilot data we observed a change in SV of 12.5mL/m^2 or higher with TNF inhibitor treatment in patients with RA.

Based on preliminary data RA patients had an LV mass of 120± 27 grams while normal people had an LV mass of 147

$\pm 40$  gram. For a change in left ventricle mass from 120 to 147 grams over the 6 month period we will have an 80% power to detect this improvement of LV mass in 25 patients treated with TNF inhibitor with a one sided alpha of 0.05 assuming a correlation of 0.35. We will have more than 85% power to detect a difference of 27 grams of mass between the TNF inhibitor treated group and the triple therapy treated group.

For changes in FDG uptake indicative of myocardial inflammation we assume that according to AHA guidelines a significant change in the intensity of FDG uptake would be equal to a decrease of 50%. We will have more than 80% power to detect such a difference between the TNF inhibitor treated group and the triple therapy treated group after 6 months of treatment with a 2 sided alpha of 0.05.

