All analyses will be performed with STATA statistical software, version 9.0 (STATA Corp, College Station, TX) and PLINK (<http://pngu.mgh.harvard.edu/~purcell/plink>). In all tests, a two-tailed alpha error of 0.05 will be defined as the level of statistical significance.

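### Do the prevalence margins in section 2b (±17.9% and ±10.7%) rest on a sample size the trial does not have?

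*Combined protocol and SAP*

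**What the plan says.** The passage is in section 2b (Sample size and power calculations). It describes what the follow-up part of the study will yield for three groups: "25 RA patients treated with TNF-antagonist, 25 RA patients treated with triple treatment or alternative, and 15 non-RA participants". It then gives two statements of precision.

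- The first is for the correlation between repeated measurements and opens with "Even accounting for a possible 15% drop out rate of participants". The margins are "within +/- 0.33 for a correlation of 0.50 and within +/- 0.09 for a correlation of 0.90".
- The second is for binary outcomes: "our estimate will be ranged approximately from within +/- 17.9% for a prevalence of 50% to +/-10.7% for a prevalence of 90" per cent. It names no group, no n and no confidence level.

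The sentence after these turns to power for a within-group change and does give its inputs: "with a 2-sided alpha of 0.05 and N=22 (accounting for possible drop out"). The end of section 2a sets the general level for tests: "a two-tailed alpha error of 0.05 will be defined as the level of statistical significance". Neither section gives a confidence level for descriptive intervals.

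**The concern.** A reader who sees a two-sided 0.05 throughout will take the margins as 95% intervals and look for the n behind them. The two figures agree with each other, and both give n=30. The trial has no group of 30, before or after dropout. The natural suspicion is that the margins came from another design or a superseded sample size. If so, the precision claimed for one RA arm is too favourable: by 3.0 percentage points at a prevalence of 50% and by 1.8 points at 90%, if n=22 and 95% were meant. Section 2b presents these estimates partly as input for planning later studies, so an overstated precision could mislead someone about how much this trial will teach.

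**Working it through.** **Inputs, all from section 2b unless noted.** Stated half-widths h: 0.179 at p=0.50 and 0.107 at p=0.90. Groups: 25, 25 and 15, which pool to 40, 50 or 65. Dropout: 15%. The two-sided 0.05 for tests is in section 2a.

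**Formula.** The usual large-sample (Wald) half-width is h = z·√(p(1−p)/n), so n = p(1−p)·(z/h)².

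**Step 1: 95% (z = 1.960).**
- p=0.50: 0.25 × (1.960/0.179)² = 29.97
- p=0.90: 0.09 × (1.960/0.107)² = 30.20

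n=30 gives 17.89% and 10.74%, which reproduces both figures. The available sizes are 15, 25, 40, 50 and 65 before dropout. After 15% dropout they are 12.75, 21.25, 34, 42.5 and 55.25. None is 30.

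| n | 95% margin at 50% | 95% margin at 90% |
|---|---|---|
| 21 | 21.4% | 12.8% |
| 22 | 20.9% | 12.5% |
| 25 | 19.6% | 11.8% |
| 30 | 17.9% | 10.7% |
| 34 | 16.8% | 10.1% |
| 42 | 15.1% | 9.1% |
| 55 | 13.2% | 7.9% |

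At n=22 the ratios to the stated margins are 20.89/17.9 = 1.167 and 12.54/10.7 = 1.172. Wilson, Agresti–Coull, Clopper–Pearson, t-based and continuity-corrected intervals at 95% were tried at sizes between 21 and 55. None gives both stated figures at a size the trial has.

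**Step 2: 90% (z = 1.645).**
- p=0.50: 0.25 × (1.645/0.179)² = 21.11
- p=0.90: 0.09 × (1.645/0.107)² = 21.27

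One RA arm after the plan's dropout is 25 × 0.85 = 21.25. The resulting margins are:
- n=21.25, z=1.645: 17.84% and 10.70%
- n=21, z=1.645: 17.95% and 10.77%
- n=21, z rounded to 1.64: 1.64 × √(0.25/21) = 17.89% and 1.64 × √(0.09/21) = 10.74%, which round to the stated pair
- n=22, z=1.645: 17.53% and 10.52%

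The figures can therefore be reached from a listed group and the stated dropout, with one unstated assumption: a 90% level.

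**Step 3: cross-check on the neighbouring correlation margins (±0.33 at r=0.50, ±0.09 at r=0.90).** With Fisher's z and standard error 1/√(n−3), at n=22:
- 95%, average of the two arms of the interval: 0.331 and 0.094
- 95%, larger arm: 0.401 and 0.129
- 90%, average: 0.279 and 0.077
- 90%, larger arm: 0.330 and 0.101

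Only the averaged 95% version fits both stated values. The plan does not say that it averaged.

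**Step 4: what depends on the prevalence margins.** The power statements that follow in section 2b carry their own n, alpha and effect sizes and take nothing from this sentence. The margins enter no test, endpoint or stopping decision.

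**The case for a change.** The best argument for changing the plan is that the 90% reading is a fit found after the fact. No 90% interval is mentioned anywhere, and the adjacent correlation margins fit n=22 at 95%, so two neighbouring statements would use different levels without saying so. Trying levels until one fits is also a loose method: at 80% the implied n is 12.8 to 12.9, close to the 12.75 controls left after dropout. The word for approximation in the sentence does not cover a gap of 3 points in figures given to one decimal.

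Much of this stands. The origin of the margins cannot be settled from the documents, and the sentence ought to have carried its n and level. The argument stops short of showing an error, though. The 95% level is brought in by the reader, since sections 2a and 2b attach 0.05 to tests, comparisons and power. A critical value of 1.645 is not foreign to section 2b either, because the left ventricular mass calculation uses a one-sided alpha of 0.05. The correlation check concerns a different estimator and fits only under an averaging convention that the plan does not state. It is suggestive and no more.

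**Conclusion.** The omission is real, but no error is demonstrated. The stated pair is consistent with a 90% interval on one RA arm after 15% dropout (n about 21), or with a 95% interval at n=30, which is no listed group. If one RA arm at 95% and n=22 was meant, the margins should be about ±20.9% and ±12.5%, and the stated ones are then too narrow by 3.0 and 1.8 points. That size rests on two assumptions that the documents do not confirm, the level and the group.

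Under any of these readings the trial enrols the same patients, runs the same tests and reaches the same conclusions. At reporting, the analyst will compute each prevalence interval from the observed count and denominator and label its level. Anyone planning a later study would use those intervals and not this forecast. Labelling the sentence would make it tidier and change nothing the trial does, so the plan can stand as it is.

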Linear mixed effects (MIXED) regression models will be used to assess trends in LV structure and functional outcomes over time between the two visits for the patients who will undergo randomization reevaluation with PET-CT and 3D Echocardiogram, while controlling for potential confounders. The data will include PET-CT studies for 25 RA patients receiving TNF antagonists and 25 RA patients receiving alternative treatment, and PET-CT studies for 15 non-RA patients. The data are longitudinal since LV outcomes are measured for each person at 2 different time points. Since repeated measures tend to be correlated within a person, mixed models with both fixed and random effects will be used to adjust for this correlation. We will use unstructured correlation structure given that each visit will occur roughly around a fixed time since study visit I, and use robust standard error estimates to conduct statistical inferences. To study the TNF inhibitor effects on LV structure or functional outcomes, visit-specific indicators, RA status, TNF treatment status, and visit x TNF treatment interaction will form the bases for the mean model. The visit-specific indicators will capture the time trend of LV outcomes over the study period, the RA status will delineate the overall mean difference in LV outcomes between RA and non-RA, with the TNF treatment status indicator and its interaction with visit indicators capturing the baseline difference in LV outcomes between TNF treated and non-treated groups and the potential TNF treatment effect on LV outcome over time, respectively. Actual TNF inhibitor dosage could be used in place of TNF status indicator in the model if necessary, and other potential covariates could be added into the model for confounding adjustment. For example, inflammation markers could be added into the model to examine whether any TNF treatment effect is mediated through the change in systemic inflammation. Similar modeling approaches can be used to study all research questions of interest using the corresponding outcomes and their hypothesized predictors listed in those questions to be addressed. For any binary outcomes in this type of regression analysis, e.g. indicator of whether a LV outcome exceeding certain critical value, generalized linear mixed effects models (GLIMMIX) can be used to study the odds of such outcome as a function of the independent variables.

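### The only between-group power figure for stroke volume is for a three-group F-test that includes untreated non-RA controls, not for TNF inhibitor versus triple therapy, and its inputs are mislabelled or unstated

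*Combined protocol and SAP*

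**What the plan says.** Section 2b plans for three groups: "25 RA patients treated with TNF-antagonist, 25 RA patients treated with triple treatment or alternative, and 15 non-RA participants". It bases the between-group power on "comparing the changes between those groups with one way ANOVA assuming a 15% drop out and a 2-sided alpha of 0.05". Two statements of 80% power follow. The first is general and has no unit: "We will have 80% power to detect any set of 3 group differences/changes if the SD of the changes is 0.444 or greater". The second is on the SV scale: a mean 24-week change of 5.2 mL/m² in the TNF inhibitor group, "while the mean change for the other two groups is 0".

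The SD of 4.2 mL/m² and the correlation of 0.2 appear earlier in the same paragraph, as an example for the change within the TNF inhibitor group. They are not restated for the ANOVA.

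Section 2a asks, for aim 2, whether TNF inhibitors act differently from the alternative therapy. It plans a linear mixed model in which "visit-specific indicators, RA status, TNF treatment status, and visit x TNF treatment interaction will form the bases for the mean model". It also says that the 15 controls receive no intervention between visits and are there to show normal variation over time. Section 2b gives two-arm power (TNF inhibitor versus triple therapy) for LV mass and FDG uptake, but not for SV.

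**The concern.** An omnibus F-test answers whether any of three group means differs. The randomised question is whether two particular means differ. Since the third group is neither randomised nor treated, the F-test can be significant because treated RA patients of either arm changed relative to healthy controls. The power quoted for SV therefore does not describe the comparison that aim 2 is about.

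The two figures also cannot be used as printed. Taken at face value, an SD of changes that must be at least 0.444 runs backwards, because more spread in patients' changes lowers power. The 5.2 mL/m² cannot be checked without an SD of change and a correlation for this calculation. At stake is whether a reader can tell what SV difference between the randomised arms the trial can detect.

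**Working it through.** **Inputs (section 2b).** Groups 25/25/15; 15% dropout; alpha 0.05; SV SD 4.2; correlation r = 0.2 (printed for the within-group example only). 25 × 0.85 = 21.25 and 15 × 0.85 = 12.75, so completers are 21/21/12 (rounded down), 21/21/13 (nearest) or 22/22/13 (rounded up; N = 22 is printed for the TNF inhibitor group). I carry all three.

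**SD of change.** SDc = SD × √(2(1 − r)). At r = 0.2: 4.2 × √1.6 = 5.31. At r = 0: 4.2 × √2 = 5.94. As a check, a one-sample t-test with SDc 5.31 has 80% power at 3.41 (n = 21) or 3.33 (n = 22), against 3.42 printed. The formula is therefore the plan's own.

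**The 0.444.** Read as Cohen's f (SD of group means divided by within-group SD), the noncentrality is λ = N f², with F on 2 and N − 3 df.

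| N | Power at f = 0.444 | f for 80% |
|---|---|---|
| 52 (20/20/12) | 80.0% | 0.444 |
| 54 (21/21/12) | 81.7% | 0.435 |
| 55 (21/21/13) | 82.5% | 0.431 |
| 57 (22/22/13) | 83.9% | 0.423 |

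Read as 0.444 mL/m² between group means, power is about 8%. Only the standardised reading works.

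**The 5.2/0/0 alternative.** λ = [n₁(N − n₁)/N] × (5.2/SDc)². For 22/22/13 at r = 0.2: (22 × 35/57) × (5.2/5.31)² = 12.94.

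| Completers | r = 0.2: power at 5.2 | r = 0.2: 80% at | r = 0: power at 5.2 | r = 0: 80% at |
|---|---|---|---|---|
| 22/22/13 | 88.9% | 4.61 | 80.7% | 5.16 |
| 21/21/13 | 87.6% | 4.71 | 78.9% | 5.27 |
| 21/21/12 | 87.1% | 4.74 | 78.4% | 5.30 |

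So 5.2 needs r near 0. Equal groups of 18 with r = 0.1 also give 5.20.

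**Do the two figures agree?** For one shifted group, f = (d/SDc) × √(p(1 − p)), with p = n₁/N. At SDc 5.31, f = 0.444 corresponds to d = 4.84–4.86 mL/m² for the three sets of completers (5.00 with equal groups), not 5.2.

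**Both RA arms gain 5.2, controls 0.** λ = [n₃(N − n₃)/N] × (5.2/5.31)² = 9.61 (22/22/13), 9.51 (21/21/13) or 8.94 (21/21/12). The F-test rejects in 77.5%, 76.9% or 74.1% of trials although the randomised arms do not differ.

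**Randomised contrast.** Two-sample t on change, two-sided 0.05, δ = d/(SDc√(2/n)).

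| r | n per arm | δ at 5.2 | Power at 5.2 | 80% at |
|---|---|---|---|---|
| 0.2 | 21 | 3.17 | 87.2% | 4.71 |
| 0.2 | 22 | 3.25 | 88.7% | 4.59 |
| 0 | 21 | 2.84 | 79.1% | 5.26 |
| 0 | 22 | 2.90 | 81.0% | 5.14 |

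These are almost the same as the omnibus values, so leaving the controls out costs essentially no sensitivity.

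**The planned model.** The listed terms include RA status but no visit-by-RA term. As written, the visit-by-TNF term compares change in the TNF inhibitor group with change in triple therapy and controls pooled, which matches neither the ANOVA nor the randomised contrast.

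**The case against.** The strongest reply is that the ANOVA is only a planning approximation. Section 2a assigns the TNF effect to the mixed model, the SV alternative actually powered (5.2/0/0) is one where TNF inhibitor does differ from triple therapy, and two-arm power is given for LV mass, the study's central phenotype. All of that is true. It limits the gap to SV, and it means that the 74–78% describes what the test would do in a scenario the plan does not power. It does not supply the missing SV statement.

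A reader might infer that both printed figures are arithmetic errors. The documents do not support that. As Cohen's f, 0.444 is exact at N = 52 and within 2 points of 80% at 15% dropout rounded down, and on that reading the direction of the sentence is right. For 5.2, section 2b says that it used "various values for within person correlation between outcome measures at subsequent visits" and does not say which applies here, so an unstated value near 0 may lie behind it. What stands is a wrong label and unstated inputs.

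A reader might also infer that the trial is underpowered for SV. At the printed SD and correlation the reverse holds: power at 5.2 is above the 80% claimed.

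**Conclusion.** The point holds as a mismatch between the SV power statement and the randomised question, together with a mislabelled effect size and missing assumptions. It should be corrected, but it does not change the sample size. At SD 4.2 and r = 0.2 the printed 5.2 mL/m² overstates the 80% detectable change by about 0.5–0.6 mL/m² (5.2 against 4.61–4.74), which is conservative. The randomised contrast has 87–89% power at 5.2 if r = 0.2 and 79–81% if r = 0.

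These figures assume normal changes with a common SD in all groups and 21–22 completers per RA arm. The documents settle neither the correlation nor the completer count for this comparison, so the results are ranges. Nor do they say that a three-group F-test will be used to claim a TNF effect. The risk is that the power text invites that use.

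**What to change.** Replace the two ANOVA sentences in section 2b with text such as:

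> For the 24-week change in SV, TNF inhibitor minus triple therapy, two-sided alpha 0.05, cross-sectional SD 4.2 mL/m² and 21–22 completers per arm, 80% power is reached at a difference of 4.6–4.7 mL/m² if the within-person correlation is 0.2 (87–89% power at 5.2) and at 5.1–5.3 mL/m² if it is 0 (79–81% power at 5.2).

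State which correlation and completer count the authors consider most likely and why. Delete 0.444, or label it as Cohen's f with its N. Report the controls' change separately as normal variation, and base the TNF inference on TNF inhibitor versus triple therapy, not on the three-group F-test. For the model to match, section 2a should add a visit-by-RA term or fit the treatment comparison in the two RA arms only.

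The cost is a few sentences of rewording. No visit, measurement or recruitment target changes.

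### Section 2b: the 80% within-arm LV-mass power does not follow from its printed inputs (which give 89–99.6%), and cannot share one SD with the >85% between-arm figure

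*Combined protocol and SAP*

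**What the plan says.** Section 2b takes its LV-mass inputs from preliminary data: "RA patients had an LV mass of 120± 27 grams while normal people had an LV mass of 147", the latter with a spread of 40 g. Taking the correlation between visits to be 0.35, it then claims "80% power to detect this improvement of LV mass in 25 patients treated with TNF inhibitor with a one sided alpha of 0.05". The next sentence reads "We will have more than 85% power to detect a difference of 27 grams of mass between the TNF inhibitor treated group"; the comparator is the triple therapy arm. That sentence gives no SD, n, correlation, alpha or test.

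The preceding paragraph of Section 2b works on a different basis. It allows for loss ("Even accounting for a possible 15% drop out rate of participants") and powers the within-arm changes in cardiac output and stroke volume "with a 2-sided alpha of 0.05 and N=22 (accounting for possible drop out").

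Section 2a closes with "In all tests, a two-tailed alpha error of 0.05 will be defined as the level of statistical significance". Its general paragraph on comparisons also sets two-tailed tests at 0.05, but allows exceptions where these are noted.

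**The concern.** A one-sample test on change should have more power than a comparison of two arms of the same size for the same difference. Section 2b states the reverse: 80% within the TNF arm and more than 85% between arms, both for 27 g. A one-sided test on all 25 patients, with a target as large as the RA standard deviation, should also give well over 80%.

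LV mass is the phenotype the study is built around, and the between-arm comparison is its randomised test. If the SD, N, test and sidedness behind these figures cannot be identified, a reader of a null LV-mass result cannot say what difference the trial was able to detect.

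**Working it through.** **Inputs, all from Section 2b:** change 147 − 120 = 27 g; n = 25; one-sided alpha 0.05; r = 0.35; SD 27 g (RA) and 40 g (normal). The SD used at each visit is not stated, so three pairings are tried. Dropout of 15% leaves 25 × 0.85 = 21.25; the plan itself uses 22.

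**Check of method on neighbouring figures.** For cardiac output (SD 1.8, r = 0.2, N = 22, two-sided), the SD of change is 1.8 × √(2 × 0.8) = 2.28. The noncentrality is 1.47 × √22 / 2.28 = 3.03, and power is 82.3%. Stroke volume gives 82.1%. Both are close to the stated 80%, so the method suits this section.

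**Step 1, SD of change** = √(a² + b² − 2rab):
- 27 and 27: √(729 + 729 − 510.3) = 30.78 g
- 27 and 40: √(729 + 1600 − 756) = 39.66 g
- 40 and 40: √(1600 + 1600 − 1120) = 45.61 g

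**Step 2, within-arm power at n = 25.** Noncentrality = 27 × √25 / SD of change; noncentral t with 24 df.

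| SD at visits I, II | Noncentrality | One-sided (as printed) | Two-sided | Change detectable at 80%, one-sided |
|---|---|---|---|---|
| 27, 27 | 4.39 | 99.6% | 98.8% | 15.8 g |
| 27, 40 | 3.40 | 95.2% | 90.4% | 20.3 g |
| 40, 40 | 2.96 | 89.1% | 81.1% | 23.3 g |

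The normal approximation gives 99.7, 96.1 and 90.6% one-sided, so the choice of t or z does not explain the gap.

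**Step 3, the SD that one-sided 80% would need.** Solving at n = 25 gives an SD of change of 52.7 g. With equal SDs, the SD of change is S√(2 × 0.65) = S√1.30, so S = 52.7/1.140, about 46.3 g. That exceeds both printed spreads.

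**Step 4, can the two powers share one SD?** With common SD S, n = 25 per arm and r = 0.35, the variance in units of S²/n is 1.30 for the within-arm change. Between arms it is 2.60 for change scores, 2.00 for follow-up values and 2(1 − 0.35²) = 1.755 baseline-adjusted.
- At S = 46.3 g, where the within-arm figure is 80%, between-arm power is 55.5, 65.2 and 70.1% one-sided, or 42.6, 52.5 and 57.9% two-sided.
- In reverse, the largest S giving 85% between arms is 37.5 g (baseline-adjusted, one-sided). There the within-arm one-sided power is already 92.3%.

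No common SD gives both printed figures.

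**Step 5, where more than 85% could come from.** For two-sided change scores with SD 27 g and 25 per arm, the noncentrality is 27 / (30.78 × √(2/25)) = 3.10, and power is 86.0%. With SD 40 g it is 53.6%.

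**Step 6, both figures two-sided after dropout (21–22 per arm):**

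| | SD 27 g | SD 40 g |
|---|---|---|
| Within TNF arm, change | 96.9–97.5% | 73.3–75.4% |
| Between arms, change scores | 79.2–81.1% | 46.5–48.4% |
| Between arms, follow-up values | 88.5–90.0% | 56.9–59.0% |
| Between arms, baseline-adjusted | 92–93% | not computed |

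**The case against.** Several points on the other side stand.

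- **Sidedness.** A reader might infer a plain breach of the two-tailed rule. Section 2a's closing sentence has no exception, but its general paragraph allows exceptions that are noted, and Section 2b does note one. The two statements in Section 2a differ, so this is an inconsistency, not a clear violation.
- **Dropout.** No section requires the 15% allowance in every calculation. Using 25 is disclosed and matches the 25 per arm described for the mixed-model analysis. It is only less conservative than the paragraph before.
- **The two powers.** They contradict each other only if both use one SD. Two different printed spreads bring each close to its stated value at n = 25: 81.1% within arm (SD 40 g, two-sided) and 86.0% between arms (SD 27 g, change scores, two-sided). The label of one-sided may be a slip. Even so, the printed wording would be wrong and the two sentences would rest on different, undeclared SDs.
- **Nearby readings.** If 25 means enrolled, one-sided SD 40 g gives 83.5–85.1% at 21–22 patients. That is nearer to 80% but still above it.
- **Prevalence precision.** Section 2b's half-widths of 17.9% and 10.7% match n = 30 at 95%, which is no planned group, so a reader might call them wrong. But no n, group or confidence level is stated, and a 90% interval at n = 21 gives 17.95% and 10.77%. Only missing detail is shown.

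**Conclusion.** The within-arm 80% is wrong as written. On its own inputs power is 89.1–99.6%, at least 9 points higher for every pairing of the printed spreads. At n = 25 with those spreads and the t test, about 80% appears only if the test is two-sided with SD 40 g. Given one common SD, r = 0.35 and n = 25, it cannot coexist with more than 85% between arms. So at least one figure is wrong, or the two use different SDs that the plan does not declare.

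A reader might go further and infer that the trial is underpowered for LV mass. The documents do not support that. The within-arm error understates power. Between arms with SD 27 g, change scores fall to 79–81% after dropout, but follow-up values or a baseline-adjusted analysis stay above 85%. The 47–48% result needs SD 40 g in both arms at both visits, whereas the plan's own RA spread is 27 g. The between-arm figure is uncheckable rather than shown to be false. These results assume normal-theory t tests and the stated correlation of 0.35.

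**What to change.** Remove the one-sided claim and restate both LV-mass powers two-sided at 0.05, at one post-dropout N (21–22 per arm), naming the test, SD and correlation. If change scores are meant, the text could give: SD 27 g at both visits, r = 0.35, SD of change 30.8 g; power for 27 g about 97% within the TNF arm and 79–81% between arms; with SD 40 g, 73–75% and 47–48%. The 86% figure should be kept only if labelled as 25 per arm with no dropout.

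Section 2a names a mixed model, not a change-score test: "visit-specific indicators, RA status, TNF treatment status, and visit x TNF treatment interaction will form the bases for the mean model". If that model, follow-up values or a baseline-adjusted analysis is the intended test, state that test's own power and inputs. For the mixed model this includes whether the controls have their own time trend, since the listed terms do not give them one.

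Reconcile the two statements on sidedness in Section 2a. For the prevalence precision, simply add the n, group and confidence level.

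The cost is a text change, with no extra patients or procedures. On change scores with SD 27 g, the between-arm figure becomes slightly less favourable and the within-arm figure more so.
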